We chose the above metric for protocol deviation because with complex interventions, as the frequency of monitoring increases, so does the resources required to track protocol adherence. Close monitoring of protocol deviations is unlikely in trials that lack resources, introducing a risk of ascertainment bias. In contrast, with very frequent monitoring of continuous interventions, the likelihood of recording protocol deviations increases but the clinical impact of each deviation diminishes proportionately. Similarly, criteria for protocol deviations that are too sensitive would exaggerate the impact of protocol deviations beyond what is clinically important and unduly undermine the apparent feasibility and internal validity of the trial.

All reasons for non-adherence will be recorded for both groups using pretested taxonomy distinguishing clinical reasons (*e.g.*, hypotension, hypertension, difficulty in oxygenation, respiratory distress, hemodynamic instability, attending override of protocol) and research-related reasons (*e.g.*, consent withdrawal).

3. *Recruitment rate*: A successful recruitment rate will be defined as achieving an enrollment rate of 1 patient per ICU per time window during the trial. While this feasibility trial is ongoing, recruitment will be reviewed weekly; the screening records

will be reviewed monthly, and the numbers of missed eligible patients will be investigated. If applicable, we will discuss barriers to enrollment and use well-developed strategies to improve recruitment. Therefore, recruitment will be maximized as necessary over the course of the trial. The recruitment metric will be measured and interpreted at the end of the trial by calculating the mean number (standard deviation) of recruited patients per active screening month.

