## 6 STUDY POPULATION AND ENROLLMENT

### 6.1 SETTING

The trial will accrue a maximum of 112 patients. Participants will be enrolled from 5 ICUs at the UPMC, Pittsburgh, PA, and 5 ICUs at the Mayo Clinic, Rochester, MN. At the UPMC, we will include the Transplant ICU, Medical ICU, and the Surgical Trauma ICU at the Presbyterian hospital, and the Medical-surgical ICU and Neuro-ICU (ICU8) at the Mercy hospital. At Mayo Clinic, we will enroll at the Medical-surgical ICU from the Methodist campus, and the Cardiac, Medical, Surgical, and CV Surgery ICUs at St. Mary's campus. No study ICU has a protocolized approach to fluid removal, and instead, clinicians determine the timing and rate of UFNET. All ICUs use specialized ICU nurses trained and certified in delivering CKRT. We expect each ICU to recruit one or more subjects per time window based on annual volume and past enrollment, allowing complete enrollment in 2.0 years.

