### 6.3.2 RANDOMIZATION UNIT

Following best practice recommendations for evaluation of system-level interventions, the unit of randomization is the cluster (*e.g.*, ICU) rather than the individual patient. During the first six months of data collection, all sites will continue with a liberal UFNET rate strategy. Thereafter, one ICU will be randomized to deploy the restrictive UFNET rate strategy every two months or when a maximum of 10 patients have been enrolled, whichever occurs first, and stay in this strategy until the end of the study (Figure 6).

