**Figure 6: Stepped-wedge cluster-randomized trial design**

We will use a computer-generated randomization scheme to determine the order in which each ICU would cross over from the liberal group to the restrictive group, with new crossover occurring every two months or whenever 10 patients have been enrolled, whichever occurs first. This trial design will allow us to stagger the implementation of the restrictive UFNET strategy while maintaining concurrent control over data collection in the ICUs that were not yet using the restrictive UFNET strategy.

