## 9 STATISTICAL CONSIDERATIONS

**NOTE: Detailed statistical analysis plan (SAP) will be a separate document**

### 9.1 STATISTICAL METHODS

The primary feasibility outcomes are between-group difference in mean  $UF_{NET}$  rate, protocol adherence, and recruitment rate. The primary objective of this feasibility trial to measure a minimum of 0.53-0.57 mL/kg/h separation in the delivered patient mean  $UF_{NET}$  rates between the restrictive and liberal  $UF_{NET}$  rate groups. We estimated that, if each of the 10 ICUs enrolled a minimum of 0.93 patient per 2 months for 24 months, we would have a total of 111 patients. Using the sample size calculation for SW-CRT design, we estimated that 111 patients will have 80% power at a two-sided alpha of 0.05 to reject the null hypothesis that the average  $UF_{NET}$  rate was at least 0.53-0.57 mL/kg/h different between the two groups, using intra-cluster correlation coefficient of 0.01, at a standard deviation of 0.75, and assuming mean  $UF_{NET}$  rate of 1.0 mL/kg/h (Table 6). After accounting for a very small attrition rate, we plan to recruit from each of the 10 ICUs: 1 patient per 2 months for 24 months for a total of 112 subjects or 56 patients per group.

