#### 4.2.3 RECRUITMENT RATE

A successful recruitment rate will be defined as achieving an enrollment rate of 2 patients per month per center during the trial. The recruitment metric will be calculated as the mean number (standard deviation) of recruited patients per active screening month.

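### The recruitment success threshold, a primary feasibility outcome, differs between protocol and SAP, and the protocol's stated accrual rate gives 120 patients, not 112

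*Protocol*

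**What the plan says.** The protocol gives the recruitment criterion in the Executive Summary, in the Trial Summary and in section 5.8.1, item 3. The last of these defines success as "achieving an enrollment rate of 1 patient per ICU per time window during the trial". The same item says the result will be obtained by "calculating the mean number (standard deviation) of recruited patients per active screening month", without saying whether that is per ICU, per center or overall.

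Protocol 9.1 bases the sample size on the supposition that "each of the 10 ICUs enrolled a minimum of 0.93 patient per 2 months for 24 months", giving 111 patients. After a very small, unquantified attrition allowance, it plans from each of the 10 ICUs "1 patient per 2 months for 24 months for a total of 112 subjects or 56 patients per group". Section 6.1 makes 112 a maximum, expects at least one patient per ICU per window, and describes this as "allowing complete enrollment in 2.0 years".

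On the calendar, section 6.3.2 says "During the first six months of data collection, all sites will continue with a liberal" rate strategy. The text with Figure 6 then describes the steps: "with new crossover occurring every two months or whenever 10 patients have been enrolled, whichever occurs first".

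SAP 4.2.3 defines success as "achieving an enrollment rate of 2 patients per month per center during the trial", and SAP section 3 gives the same rate. The SAP describes a two-center trial of 144 patients in 6 ICUs. Its shell Table 2 (Appendix C) reports recruitment per month per site.

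**The concern.** A feasibility outcome with a success threshold needs one rule that two analysts would apply in the same way. Here the two documents set different bars in different units. The protocol's unit, the time window, has no stated length in the readable text. The protocol's one sentence linking rate, duration and total also does not multiply out.

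The stake is the reported verdict on one of the three outcomes meant to support a phase III trial. If the rule is not fixed beforehand, the same enrolment count can be reported as success or failure, and the choice could be made with the count in view.

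**Working it through.** **Inputs.** 10 ICUs, 5 per center, two centers (Protocol 6.1); 24 months (Protocol 6.1 and 9.1); rates of 0.93 and 1 per ICU per two months (Protocol 9.1); maximum 112 (Protocol 6.1); SAP rate of 2 per month per center (SAP 3 and 4.2.3).

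**Assumptions.** A time window is two months, inferred from the step interval in 6.3.2 and the planned rate in 9.1. *Center* means hospital system, in line with the SAP's own description of the trial as two-center.

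**1. The protocol's accrual figures.** Total = ICUs × rate × number of two-month periods, with 24/2 = 12 periods.

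- Minimum rate: 10 × 0.93 × 12 = 111.6. This reproduces the stated 111.
- Planned rate: 10 × 1 × 12 = 120. The stated 112 is not reproduced; the gap is 8 patients.
- Working back: 112/(10 × 12) = 0.933 per ICU per two months.
- At a rate of 1, accrual is 10/2 = 5 per month, so 112 is reached at 112/5 = 22.4 months.

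Attrition does not close the gap. Going from 111 to 112 is a rise of 0.9% (112/111 = 1.009); going from 0.93 to 1 is a rise of 7.5% (1/0.93 = 1.075). No single allowance gives both.

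**2. The two thresholds on the protocol's design (10 ICUs, two centers, 24 months).**

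- Protocol rule: 1 × 10 × 12 = 120 patients, or 120/(2 × 24) = 2.5 per center per month.
- SAP rule: 2 × 2 × 24 = 96 patients, or 96/120 = 0.80 per ICU per two months.

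| Total in 24 months | Per ICU per 2 months (total/120) | Protocol rule (at least 1) | Per center per month (total/48) | SAP rule (at least 2) |
|---|---|---|---|---|
| 96 | 0.800 | fails | 2.00 | met |
| 111 | 0.925 | fails | 2.31 | met |
| 112 | 0.933 | fails | 2.33 | met |
| 120 (above the cap) | 1.000 | met | 2.50 | met |

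Totals of 96 to 119 pass one rule and fail the other. With the cap, the reachable part of that band is 96 to 112.

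**3. Counting the baseline.** At an even pace of 112/24 = 4.67 per month, the six-month baseline brings 28 patients (2.8 per ICU) and each two-month step 9.33 (0.933 per ICU).

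- Baseline counted as three two-month windows, plus nine steps: 12 windows, 112/120 = 0.933, criterion missed.
- Baseline counted as one window, plus nine steps (6 + 18 = 24 months): 10 windows, 112/100 = 1.12, criterion met.
- Baseline counted as one window, plus ten steps: 11 windows, 112/110 = 1.02, criterion met. This takes 6 + 20 = 26 months unless some steps close early.

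**4. Sample size.** The power statement takes 111 patients as its input. With one baseline period, ten steps, SD 0.75 and ICC 0.01, the Hussey-Hughes formula gives a detectable difference of 0.525 at 80% power, close to the stated 0.53. Correcting the recruitment wording changes neither N nor the power statement.

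**The case against.** The strongest reply is that the plan does not have to miss its own bar. The figure of 112 is a cap, and section 6.1 expects one or more patients per ICU per window. At the planned rate the cap is reached at 22.4 months, inside two years, and the criterion is met. This stands: failure at 0.933 arises only if 112 patients take the full 24 months. A reader might infer that the enrolment plan is bound to fail its criterion; the documents do not support that.

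Other stronger readings also fall away.

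- **0.93 against 1.** These do not conflict by themselves. Section 9.1 calls 0.93 a minimum, and planning above a minimum is normal. The error is in the total attached to the rate of 1.
- **The 10-patient rule.** It does not put the criterion out of reach. If the rule is trial-wide (an assumption), a step closed at 10 patients gives 10/10 = 1 per ICU, which meets it.
- **Center read as ICU.** That would set an SAP bar of 2 × 10 × 24 = 480, but it contradicts the SAP's two-center wording.

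The missing definition of the window may lie in Figure 6, which is not shown in the text reviewed. The window may have been meant as a design period, with one baseline and ten steps: 110 ICU-periods, close to 112. The SAP's allocation table (Appendix D, Figure 3) likewise treats the baseline as a single Step 0 and plans counts by ICU and step, although it is drawn for 6 ICUs. This is a fair reading, but it needs 26 months unless steps close early. The nine-step version that fits 24 months places the tenth crossover at month 6 + 9 × 2 = 24, leaving that ICU no restrictive period. Neither is therefore a clean alternative result. They show that the counting rule matters, and neither makes 10 × 1 × 12 equal 112.

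Finally, the SAP mismatch is probably part of a wider failure to update it from 6 ICUs and 144 patients, and applying its rate to 10 ICUs over 24 months produces a hybrid that neither document describes. That explains the conflict without removing it: Protocol section 9 leaves the detailed analysis to a separate SAP, and the one supplied carries a different success rule for a primary outcome.

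**Conclusion.** The point holds, and should be fixed.

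Two errors stand in the text. Protocol 9.1 attaches a total of 112 to a rate that yields 120. The success threshold for a primary outcome also differs between protocol and SAP. On two-month windows, two centers and 24 months, the bars are 120 and 96 patients (2.5 and 2.0 per center per month). The planned 112, if it takes the full 24 months, falls between them: 0.933 per ICU per two months misses the protocol rule, and 2.33 per center per month meets the SAP rule.

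A third weakness follows from the units. The threshold is per ICU per window, the metric is per screening month, and windows run from six months at baseline to two months or less afterwards, so the way the baseline is counted can change the verdict.

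The arithmetic error needs no assumption. The pass/fail comparison depends on the inferred two-month window and on center meaning hospital system. A reader might go on to infer that the trial is undersized; nothing here supports that.

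**What to change.** Before recruitment results are interpreted:

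- State one threshold in fixed calendar units in both documents. Rates that match 112 in 24 months are 112/240 = 0.467 per ICU per month or 112/48 = 2.33 per center per month. Alternatively, keep 1 per ICU per two months and state that it requires 112 patients within 22.4 months. The choice is the sponsor's.
- Define the time window in text if the term is kept, and say how the six-month baseline and any step closed early at 10 patients are counted.
- Compute and report the metric in the threshold's own unit.
- Correct the sentence in Protocol 9.1 so that rate, duration and total agree.
- Update SAP sections 3 and 4.2.3 to the 10-ICU, 112-patient design, and say that center means hospital system if that is intended.

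The cost is wording in two documents and one sponsor decision. Nothing operational changes, and N and power stay as they are.

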#### 5.8.2 SECONDARY OUTCOMES

1. Daily fluid balance
2. Cumulative fluid balance
3. Duration of kidney replacement therapy
4. Duration of mechanical ventilation
5. Organ failure free days
6. ICU length of stay
7. Hospital length of stay
8. Hospital mortality
9. Dependence on kidney replacement at hospital discharge

#### 5.8.3 SAFETY OUTCOMES

1. Intradialytic hypotensive episodes
2. Intradialytic hypertensive episodes
3. Intradialytic new onset cardiac arrhythmias including supraventricular tachycardia, bradycardia, atrial fibrillation, ventricular tachycardia, ventricular fibrillation, and cardiac arrest
4. Emergent use of rescue UFNET with rates higher than the assigned treatment arm
5. Severe hypophosphatemia (<0.5 mg/dL)
6. Severe hypokalemia (<3.0 mg/dL)
7. Severe hypocalcemia (<1.90 mg/dL or ionized calcium <0.90 mmol/L)
8. CKRT system downtime due to hemofilter clotting or clogging
9. Discontinuation of UFNET due to hemodynamic instability
10. Inability to close surgical wounds due to edema
11. New organ dysfunction
12. Worsening of systolic or diastolic cardiac function on echocardiogram
13. Worsening of pulmonary edema on chest X Ray and or/or CT scan
14. Worsening of ileus on abdominal X Ray and/or CT scan
15. Bowel ischemia or anastomotic breakdown based on intraoperative findings
16. Pressure ulcerations
17. New wound infections
18. New arterial or venous thrombosis
19. Severe anemia requiring red cell transfusions
20. Severe thrombocytopenia requiring platelet transfusions
21. New secondary infections

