- New organ dysfunction such as diastolic and systolic dysfunction on echocardiogram; pulmonary edema on chest X ray; ileus, bowel ischemia, anastomotic break down; wound infection, and pressure ulceration; arterial and venous thrombosis; severe anemia requiring red cell transfusions, and severe thrombocytopenia requiring platelet transfusions.
- New secondary infections

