#### 3.5.3 SAFETY OUTCOMES

1. No. of intradialytic hypotensive episodes
2. No. of intradialytic hypertensive episodes
3. No. of intradialytic new onset cardiac arrhythmias including supraventricular tachycardia, bradycardia, atrial fibrillation, ventricular tachycardia, ventricular fibrillation, and cardiac arrest
4. No. of participants with emergent use of rescue  $UF_{NET}$  with rates higher than the assigned treatment arm
5. No. of participants with severe hypophosphatemia ( $<0.5$  mg/dL)
6. No. of participants with severe hypokalemia ( $<3.0$  mg/dL)
7. No. of participants with severe hypocalcemia ( $<1.90$  mg/dL or ionized calcium  $<0.90$  mmol/L)
8. No. of episodes of stopping CKRT due to filter clotting or clogging
9. No. of participants with discontinuation of  $UF_{NET}$  due to hemodynamic instability
10. No. of participants in whom surgical wounds are left open due to edema
11. No. of participants with new organ dysfunction
12. No. of participants with worsening of systolic or diastolic cardiac function on echocardiogram
13. No. of participants with worsening of pulmonary edema on chest X Ray and/or CT scan
14. No. of participants with worsening of ileus on abdominal X Ray and/or CT scan
15. No. of participants with bowel ischemia or anastomotic breakdown based on intraoperative findings
16. No. of participants with pressure ulcerations
17. No. of participants with new wound infections
18. No. of participants with new arterial or venous thrombosis
19. No. of participants with severe anemia requiring red cell transfusions

20. No. of participants with severe thrombocytopenia requiring platelet transfusions
21. No. of participants with new secondary infections

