## 5 APPENDICES

### 5.1 APPENDIX A: OUTCOME VARIABLES AND ANALYSIS METHOD

Variable	Outcome Category	Scale	Analysis Method
Between-group separation in mean delivered UF NET rates	Primary	Continuous	GLMM
Protocol deviation	Primary	Binary	Wald-test for GLMM
Recruitment rate	Primary	Continuous	GLMM
Daily fluid balance	Secondary	Continuous	GLMM
Cumulative fluid balance	Secondary	Continuous	GLMM
Duration of kidney replacement therapy	Secondary	Continuous	GLMM
Duration of mechanical ventilation	Secondary	Continuous	GLMM
Organ failure free days	Secondary	Continuous	GLMM
ICU length of stay	Secondary	Continuous	GLMM
Hospital length of stay	Secondary	Continuous	GLMM
Hospital mortality	Secondary	Binary	Wald-test for GLMM
Dialysis dependence at hospital discharge	Secondary	Binary	Wald-test for GLMM
Hypotensive episodes	Safety	Continuous	GLMM
Hypertensive episodes	Safety	Continuous	GLMM
Cardiac arrhythmias	Safety	Continuous	GLMM
Emergent use of rescue UF NET rates	Safety	Binary	Wald-test for GLMM
Severe hypophosphatemia	Safety	Binary	Wald-test for GLMM
Severe hypokalemia	Safety	Binary	Wald-test for GLMM
Severe hypocalcemia	Safety	Binary	Wald-test for GLMM
CKRT stopping due to hemofilter clotting or clogging	Safety	Continuous	GLMM
Discontinuation of fluid removal due to hemodynamic instability	Safety	Binary	Wald-test for GLMM
Inability to close surgical wounds	Safety	Binary	Wald-test for GLMM
New organ dysfunction	Safety	Binary	Wald-test for GLMM
Worsening systolic/diastolic cardiac function	Safety	Binary	Wald-test for GLMM

Worsening pulmonary edema	Safety	Binary	Wald-test for GLMM
Worsening of ileus	Safety	Binary	Wald-test for GLMM
Bowel ischemia or anastomotic breakdown	Safety	Binary	Wald-test for GLMM
Pressure ulcerations	Safety	Binary	Wald-test for GLMM
New wound infections	Safety	Binary	Wald-test for GLMM
New arterial or venous thrombosis	Safety	Binary	Wald-test for GLMM
Severe anemia	Safety	Binary	Wald-test for GLMM
Severe thrombocytopenia	Safety	Binary	Wald-test for GLMM
New secondary infections	Safety	Binary	Wald-test for GLMM

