### 5.2.2 OTHER VARIABLES

We will use following criteria to adjudicate safety outcomes from intervention initiation to 12 hours following discontinuation of CRKT.

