#### *5.2.2.7 New organ dysfunction due to fluid overload*

New and worsening organ dysfunction will be assessed based on SOFA scoring. For instance, a patient with CV SOFA score of 3 at study initiation and now has score of 4 will be counted as worsening CV dysfunction. We will also capture new diastolic/systolic dysfunction on echocardiogram, pulmonary edema on chest X ray/CT scan, ileus on abdominal X ray/CT scan, bowel ischemia and anastomotic breakdown on CT scan/OR, transaminitis or hyperbilirubinemia; delirium using delirium scores on medical records, poor wound healing, wound infection, and pressure ulceration per nursing records, new onset arterial and venous thrombosis as documented by imaging and clinical examination, and anemia, hemolysis and thrombocytopenia as documented in the laboratory studies.

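### Safety outcome 15 (bowel ischemia or anastomotic breakdown) has two case definitions, operation only and CT or operation, and the analysis row does not say which governs

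*Protocol*

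**What the plan says.** **Listed outcome.** Item 15 in Protocol section 4 (Safety Outcomes) and in Protocol 5.8.3 reads "Bowel ischemia or anastomotic breakdown based on intraoperative findings". SAP 3.5.3 turns it into a participant count with the same restriction: "No. of participants with bowel ischemia or anastomotic breakdown based on intraoperative findings".

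**Adjudication text.** SAP 5.2.2 opens with "We will use following criteria to adjudicate safety outcomes from intervention initiation to 12 hours following discontinuation of CRKT". Within it, 5.2.2.7, whose title concerns new organ dysfunction due to fluid overload, includes "bowel ischemia and anastomotic breakdown on CT scan/OR".

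**Adverse-event collection.** Protocol 13.1 lists "ileus, bowel ischemia, anastomotic break down; wound infection, and pressure ulceration". In the same bullet it names the echocardiogram and the chest film as sources for cardiac dysfunction and pulmonary edema, but it names none for the bowel events.

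**Analysis.** SAP Appendix A carries the row "Bowel ischemia or anastomotic breakdown" as a binary safety outcome with a Wald test from the GLMM. Shell Table 3 has a row with the same label. Neither gives a source.

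**Neighboring item.** Item 14 accepts imaging: "Worsening of ileus on abdominal X Ray and/or CT scan". Item 13 (pulmonary edema) also accepts CT.

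**The concern.** Two analysts working faithfully from these documents could report different counts for the same row. One would follow the outcome list and require an operation. The other would follow the adjudication section and accept a CT finding.

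The operation-only wording also has a cost of its own. An operation is a decision taken after the event. Protocol section 7 says that blinding is not feasible, so the decision is made by clinicians who know the ICU's current strategy. Protocol 6.1 includes both medical and surgical units, and Protocol 5.1.1 cites mortality of 40% to 60%, so it is plausible that some patients with the event never have an operation. Requiring one makes the row measure the event and the choice to operate together.

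The row matters for visibility too. Protocol 13.3.1 says that events forming the safety outcomes go into outcome reporting and are not reported again as AEs or SAEs. Table 7 sends expected, listed events to the DSMB only at its regular meetings. The outcome count is thus one of the main places where this event is seen by name.

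**Working it through.** No stated figure has to be reproduced. The check is a comparison of the texts, followed by the algebra of what the difference does.

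**1. The definitions side by side**

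| Place | Source accepted |
|---|---|
| Protocol 4, item 15 | Operation |
| Protocol 5.8.3, item 15 | Operation |
| SAP 3.5.3, item 15 | Operation |
| SAP 5.2.2.7 | CT or operation |
| Protocol 13.1 | None stated |
| SAP Appendix A row | None stated |
| SAP shell Table 3 row | None stated |

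No section ranks one definition above the other.

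**2. Could an out-of-date SAP explain it?** The SAP describes 144 patients in 6 ICUs and the Protocol 112 patients in 10 ICUs, so the SAP does lag behind in places. That does not explain this conflict, because SAP 3.5.3 and SAP 5.2.2.7 disagree with each other. Bringing the SAP's design figures into line would leave the conflict in place.

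**3. How a patient is scored on row 15**

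| Patient | Listed wording | SAP 5.2.2.7 wording |
|---|---|---|
| Found at operation, with or without CT | Event | Event |
| Shown on CT, no operation | Non-event | Event |

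The second line is where the row changes. If 5.2.2.7 defines only item 11, that patient is counted under item 11 and not under item 15. If it also adjudicates item 15, the patient is counted in both.

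**4. Effect on the count.** Let N be the number of true events in an arm, s the share confirmed at operation, and c the share shown on CT without an operation.

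- Count on the listed wording: s × N.
- Count on the CT-or-operation wording: (s + c) × N.
- Difference: c × N.
- Between-arm ratio on the listed wording: (s_R × N_R) / (s_L × N_L) = (s_R / s_L) × (N_R / N_L), where R is restrictive and L is liberal.

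The ratio of true events is preserved if s_R = s_L and distorted by the factor s_R / s_L otherwise. The documents give no value for N, s or c. Each share could lie anywhere from 0 to 1 (with s + c at most 1), so the listed-wording count could lie anywhere from 0 to N.

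**The case against.** The strongest reply is that SAP 5.2.2.7 already governs. SAP 5.2.2 says that its criteria adjudicate the safety outcomes, the list in 5.2.2.7 broadly follows items 12 to 20, and no other entry in 5.2.2 defines item 15. On that reading the CT-shown patient is counted. This is a reasonable reading and it may be the intended one. But the section is titled as a definition of new organ dysfunction, which is item 11, and SAP 3.5.3 still carries the operation-only wording. The reply shows that the scoring is ambiguous; it does not settle it.

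A second reply is that operative confirmation is the more certain criterion. That is true, and it is why the intraoperative subset should stay visible. A third is that unblinded clinicians also decide who has a CT. This also stands: accepting CT removes the dependence on the decision to operate, but not every influence of unblinded care on ascertainment. A fourth is that Protocol 13.1 collects the events with no diagnostic condition and that the DSMB reviews all AEs. This limits the loss, although the new organ dysfunction composite does not show the specific event.

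Two stronger inferences are tempting, and the documents support neither.

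- **That patients with CT-proven events are scored event-free.** This holds only for row 15, and only on its literal wording. Such a patient can still appear under item 11 and on the adverse-event form.
- **That the undercount falls mainly on the liberal arm and hides its harm.** Protocol 5.1.1 and 5.1.2 do link faster removal to hypotension and ischemic organ injury. But Protocol 11.4 places bowel ischemia and anastomotic breakdown among the consequences of fluid overload, which Protocol 11.1 gives as a risk of the restrictive strategy. The documents can be read in either direction, and nothing in them says that the share operated on differs by arm. Any figure for events lost would rest wholly on assumed values.

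**Conclusion.** The inconsistency is real, and it exists inside the SAP as well as between the SAP and the Protocol. The row 15 count is not determined by the plan as written. On the listed wording it also depends on a post-event decision to operate in an unblinded trial. The conclusion rests on the texts alone and needs no assumption about event rates.

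Its practical size is modest. This is one of 21 safety outcomes, Protocol 11.3 says the trial is not powered to detect differences in adverse events, and none of the three primary feasibility outcomes uses it. The size and direction of any effect on the comparison between arms cannot be determined from the documents. It is worth correcting because the row will be read descriptively, and a descriptive count needs a single case definition.

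**What to change.** Adopt one definition of outcome 15, bowel ischemia or anastomotic breakdown shown on CT scan or at operation, as SAP 5.2.2.7 already has it. Use it in Protocol sections 4 and 5.8.3, SAP 3.5.3, the Appendix A row and the shell Table 3 row. State in SAP 5.2.2 that it adjudicates item 15 as well as contributing to item 11. Record the source for each case (CT, operation or both) so that the intraoperative subset can be reported beside the full count.

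The cost is one phrase in three lists, a label in two tables, a sentence in the SAP and one field on the case report form. CT reports are already a source for items 13 and 14. The downside is that CT-only cases are somewhat less certain; the recorded source lets a reader set them aside.
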